12.4. Adverse Event Classification

Adverse Event Severity

Ear-related adverse events will be classified as to the severity of the event based on the definitions consistent with AE severity grading scale provided by the National Cancer Institute, of the NIH and US Department of Health and Human Services – Common Terminology Criteria for Adverse Events v.4.03 (CTCAE) June 14, 2010 (**Table 5**).⁶⁶ Grade level of adverse event refers to the severity of the event. [REDACTED]

[REDACTED]

[REDACTED]

[REDACTED]

Table 5. Table of Ear-related Adverse Event Severity

Adverse Event	Grade 1	Grade 2	Grade 3	Grade 4	Grade 5
Ear pain	Mild pain	Moderate pain; limiting instrumental activities of daily living (ADL)	Severe pain; limiting self care ADL	-	-
External ear inflammation	External otitis with erythema or dry desquamation	External otitis with moist desquamation, edema, enhanced cerumen or discharge; tympanic membrane perforation; tympanostomy	External otitis with mastoiditis; stenosis or osteomyelitis; necrosis of soft tissue or bone	Urgent operative intervention indicated	Death
External ear pain	Mild pain	Moderate pain; limiting instrumental ADL	Severe pain; limiting self care ADL	-	-
Middle ear inflammation	Serous otitis	Serous otitis, medical intervention indicated	Mastoiditis; necrosis of canal soft tissue or bone	Life-threatening consequences; urgent intervention indicated	Death
Tinnitus	Mild symptoms; intervention not indicated	Moderate symptoms; limiting instrumental ADL	Severe symptoms; limiting self care ADL	-	-
Vertigo	Mild symptoms	Moderate symptoms; limiting instrumental ADL	Severe symptoms; limiting self care ADL	-	-
Vestibular disorder	-	Symptomatic; limiting instrumental ADL	Severe symptoms; limiting self care ADL	-	-
Ear - Other	Asymptomatic or mild symptoms; clinical or diagnostic observations only; intervention not indicated	Moderate; minimal, local or noninvasive intervention indicated; limiting age-appropriate instrumental ADL	Severe or medically significant but not immediately life-threatening; hospitalization or prolongation of existing hospitalization indicated; disabling; limiting self care ADL	Life-threatening consequences; urgent intervention indicated	

Table 6. Table of Other Events Adverse Event Severity

Adverse Event	Grade 1 (Mild)	Grade 2 (Moderate)	Grade 3 (Severe)	Grade 4 (Potentially Life Threatening)

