Nausea/Vomiting	No interference with activity or 1-2 episodes/24 hours	Some interference with activity or >2 episodes/24 hours	Prevents daily activity, requires outpatient IV hydration	ER visit or hospitalization for hypotensive shock
Diarrhea	2-3 loose stools or <400 gms/24 hours	4-5 stools or 400-800 gms/24 hours	6 or more watery stools or >800 gms/24 hours or requires outpatient IV hydration	ER visit or hospitalization
Headache	No interference with activity	Repeated use of non-narcotic pain reliever > 24 hours or some interference with activity	Significant; any use of narcotic pain reliever or prevents daily activity	Significant; prevents daily activity
Fatigue	No interference with activity	Some interference with activity	Significant; prevents daily activity	Significant; prevents daily activity
Myalgia	No interference with activity	Some interference with activity	Significant; prevents daily activity	Significant; prevents daily activity
Illness or clinical adverse event	No interference with activity	Some interference with activity not requiring medical intervention	Prevents daily activity and requires medical intervention	Significant; prevents daily activity

Other adverse events (**Table 6**) will be classified as to the severity of the event based on the definitions consistent with AE severity grading scale provided by FDA Guidance (Sep 2007) entitled “Toxicity Grading Scale for healthy Adult and Adolescent Volunteers Enrolled in Preventive Vaccine Clinical Trials”.⁶⁷ Grade level of adverse event refers to the severity of the event.

Any increase in the severity of an AE should be documented.

Adverse Event Causality

Causality regarding device, drug and/or procedure relationship will be assigned by the Investigator to all adverse events according to the definitions provided in **Table 7**.

Table 7. Table of Adverse Event Causality

Causality	Description*
Certain	A clinical event, including laboratory test abnormality, occurring in a plausible time relationship to procedure, device or drug administration/exposure, which cannot be explained by concurrent disease, other interventions or other drugs and considered definitely related to the study drug, device or procedure.
Probable	A clinical event, including laboratory test abnormality, with a reasonable time sequence to procedure, device or drug administration/exposure, unlikely to be attributed to concurrent disease, other interventions or drugs.

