15.2. Study Stopping Criteria

The Sponsor or Investigator may terminate the study or center participation at any time for reasonable cause, and will provide sufficient notification.

Reasons for premature suspension of the trial include, but are not limited to:

- Risk to Subjects

- Lack of effectiveness [REDACTED]
- Inadequate enrollment
- Business reasons

Reasons for premature termination of an investigational site include, but are not limited to:

- Site is non-compliant to protocol, procedures or GCP
- Inadequate enrollment

Reasons for premature suspension of enrollment include but are not limited to:

- 3 serious Grade 3 or higher unexpected drug, device or procedure-related adverse events.

[REDACTED]

[REDACTED]

At the point the site or study is terminated, the site will immediately invoke all procedures required at the 3-week follow-up visit.

All potential subjects in the study will be verbally informed, and will sign an informed consent in compliance with 21CFR §50 that states that study termination will neither prejudice nor in any way affect their future treatment.

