14.0 Safety Endpoint Analyses

14.1 Adverse Events

Adverse events (AEs) reported during the study will be coded using the Medical Dictionary for Regulatory Activities (MedDRA). The number and percentage of subjects reporting adverse events will be summarized by MedDRA system organ class and preferred term by cohort and in total.

The study will present the totality of safety data, by subject including:

- Serious device, procedure, and drug-related events
- Other serious events
- Non-serious device, procedure, drug-related events
- Other non-serious events

For all AE tables, a subject reporting the same AE more than once will be counted once when calculating the number and percentage of subjects with that particular event. If a subject reports the same AE more than once or has the same AE on multiple occasions, the maximum severity grade recorded for the event will be presented.

Overall summaries of serious and non-serious AEs will be presented. The overall summaries will include the number and percentage of subjects experiencing AEs classified by treatment, relationship to device/procedure/study drug, MedDRA SOC (System Organ Class) and preferred term. Summaries of AEs will also be presented by severity for each treatment group including the number and percentage of subjects experiencing AEs classified by relationship to device/procedure/study drug, SOC and preferred term.

[REDACTED]

[REDACTED]

[REDACTED]

Safety data will be presented separately as follows:

- Lead-In OR Cohort
- Lead-In Office Cohort
- Pivotal Cohort

Complete subject listings of all AEs will be provided. For each AE the following will be specified: start and stop dates, severity grade, MedDRA SOC, relationship to study device, relationship to procedure, relationship to study drug, action taken, outcome of the adverse event and seriousness. Any unanticipated adverse events will be noted.

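### In Protocol Table 6, Grade 4 is not separated from Grade 3 in four of six rows, so the Grade 3 versus Grade 4 split for those non-ear events cannot be interpreted

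*Protocol*

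**What the plan says.** Protocol section 12.4 uses two severity scales. Ear-related events go to Table 5. Other events go to Table 6, which the protocol says follows an FDA toxicity grading guidance. The last column of Table 6 is headed "Grade 4 (Potentially Life Threatening" (the closing bracket follows in the original).

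In that column, the headache, fatigue, myalgia and illness rows all carry the same text: "Significant; prevents daily activity". The Grade 3 cells beside them are:

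- Fatigue and myalgia: the same words as Grade 4.
- Headache: "Significant; any use of narcotic pain reliever or prevents daily activity".
- Illness or clinical adverse event: "Prevents daily activity and requires medical intervention".

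The grades are used in three places:

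- Protocol 13.6 summarizes event frequency by severity and takes the worst case of a repeated event.
- SAP 14.1 summarizes events by severity. For an event that a subject has more than once, "the maximum severity grade recorded for the event will be presented".
- Protocol 15.2 lists, as a reason to suspend enrollment, "3 serious Grade 3 or higher unexpected drug, device or procedure-related adverse events".

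**The concern.** A severity scale has to be ordered: each grade should describe something worse than the grade below it. Where two adjacent cells say the same thing, or the upper cell drops a condition that the lower one imposes, the grade depends on which cell the site happens to read.

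The study has a single arm, and its safety endpoint is the descriptive occurrence of adverse events, so the tabulations are the main safety evidence. An event in which a child's daily activity was prevented by fatigue, with no threat to life, could be tabulated under the potentially life-threatening label at one site and as severe at another. Protocol 12.4 also asks that any increase in severity be documented. For fatigue and myalgia, a rise from Grade 3 to Grade 4 cannot be recognized.

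**Working it through.** There is no plan figure to reproduce. The check compares the Grade 3 and Grade 4 cells as logical conditions and then follows the grade to where it is used.

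**Step 1. Conditions.** Write S for significant, P for prevents daily activity, N for any narcotic pain reliever, and M for requires medical intervention.

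| Row of Table 6 | Grade 3 | Grade 4 | Relation |
|---|---|---|---|
| Fatigue | S and P | S and P | identical |
| Myalgia | S and P | S and P | identical |
| Headache | S and (N or P) | S and P | Grade 4 lies inside Grade 3 |
| Illness | P and M | S and P | overlapping; Grade 4 drops M and adds S |
| Nausea/vomiting | prevents activity, outpatient IV hydration | "ER visit or hospitalization for hypotensive shock" | ordered |
| Diarrhea | stool count or weight, or outpatient IV hydration | ER visit or hospitalization | ordered |

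Two identical rows, one nested row and one overlapping row give 2 + 1 + 1 = 4 of 6 rows in which Grade 4 is not separated from Grade 3. The other two are ordered. None of the four affected Grade 4 cells mentions a threat to life, so none matches its column heading.

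**Step 2. How far the counts can move.** The readable text has no rule for an event that meets both cells.

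- Fatigue or myalgia: if n events meet the text, the Grade 4 count can be anything from 0 to n. The total at Grade 3 or higher stays at n.
- Headache: if n events meet Grade 3, and k of them are significant and prevent activity, the Grade 4 count can be anything from 0 to k. The total at Grade 3 or higher stays at n.
- Illness: let a be the number of events meeting S, P and M, and b the number meeting S and P but not M. Read literally, the a events can be Grade 3 or 4, and the b events are Grade 4 only. The Grade 4 count runs from b to a + b.

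The b events are the awkward ones. They go beyond Grade 2, which is "Some interference with activity not requiring medical intervention", they miss Grade 3, and they land in Grade 4. A site guided by the column heading might not accept Grade 4 and would have no Grade 3 cell to use instead.

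**Step 3. Where the grade is used.**

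- *Severity summaries (Protocol 13.6, SAP 14.1).* The Grade 3 versus Grade 4 split is affected for these four rows. If repeated reports of one event are graded 3 once and 4 once, the worst-case rule carries the 4 forward.
- *Suspension rule (Protocol 15.2).* Grades 3 and 4 are pooled. By Step 2, the pooled total for headache, fatigue and myalgia is the same under either grade. Only the b illness events could be counted or not, and only if they are also serious, unexpected and related.
- *Endpoint tests (Protocol 13.3 and 13.4, SAP 10 and 11).* None uses the severity grade.

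**The case against.** **The table may be an extraction fault.** The text was read from PDF by a program, and one string fills four consecutive Grade 4 cells, which a merged or filled-down cell could also produce. Artefacts are visible elsewhere, such as the contents list running section 12 up to 12.303. This justifies checking the original page first. It does not dispose of the point, because those artefacts lie in contents pages and redacted areas, whereas Table 6 has aligned rows whose other cells read coherently.

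**Other controls exist.** Protocol 12.3 defines life-threatening and serious events separately from the grades, and the reporting duties in sections 12.2, 12.3 and 12.5 do not turn on the Table 6 grade. The Medical Monitor reviews events and their coding (12.5). The column labels and the cited scale give some guidance. These limit the harm, but none supplies a rule for separating two identical cells.

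**Stronger readings that the documents do not support.**

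- A reader might infer that the severity tables as a whole are not valid. Ear-related events, on which the procedure acts directly, use Table 5. Hearing change has Table 8, and electrode-site erythema has its own score. Nausea/vomiting and diarrhea escalate properly. Only the Grade 3/4 boundary in four non-ear rows is at issue.
- A reader might infer that Grade 4 is generally milder than Grade 3. In fatigue and myalgia it is the same, and in headache it is a subset. Only the illness row approaches an inversion, and there Grade 4 drops the intervention condition but adds that the event is significant.
- A reader might infer that the suspension rule is compromised. An illness event would have to need no medical intervention and yet be serious under 12.3. That class is very small, and read literally such an event is Grade 4 and does count. The list in 15.2 is also expressly not exhaustive.

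**Conclusion.** As printed, four of the six rows of Table 6 do not separate Grade 3 from Grade 4, and none of the four Grade 4 cells fits the column heading. For fatigue, myalgia, headache and general illness, the Grade 3 versus Grade 4 counts in the descriptive severity summaries cannot be interpreted. For the first three rows, the pooled count at Grade 3 or higher remains usable. For illness it is usable apart from events that prevent activity without needing intervention.

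The consequence is modest. Severity is descriptive, no endpoint test depends on it, and the suspension rule is untouched except possibly by rare illness events that are also serious. The number of events involved cannot be estimated, because the documents give no rates for them.

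The conclusion rests on two assumptions: that the extracted table matches the original page, and that no blacked-out text gives a rule for events meeting both cells. How far the illness row reaches is also uncertain. Its label suggests a catch-all for other clinical events, but the readable text does not say so.

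**What to change.** Check Table 6 against the original page and against the grading scale that section 12.4 cites. If the table is confirmed as printed:

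- Reconcile the Grade 3 and Grade 4 cells of the headache, fatigue, myalgia and illness rows with each other and with the column heading. The choice of wording belongs to the sponsor and the cited scale; none is proposed here.
- Send the corrected table to the sites.
- Recheck any events already graded 3 or 4 under these rows, and illness events that prevented activity without medical intervention, whatever grade they were given.

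The cost is a small amendment touching four rows, with its IRB handling, a site notice and limited regrading. If the original page turns out to differ from the text read here, no amendment is needed.

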6.0 BACKGROUND INFORMATION AND SCIENTIFIC RATIONALE

6.1. Clinical and Technology Background

Otitis media (inflammation of the middle ear) is the most frequent diagnosis in sick children visiting pediatrician offices. Seventy-five percent of children experience at least one episode of otitis media by their third year.²

Otitis media has several variations, including acute otitis media (AOM) and otitis media with effusion (OME). AOM is characterized by acute signs and symptoms of middle ear inflammation or infection. OME is characterized by the presence of fluid in the middle ear with or without signs or symptoms of acute ear infection. The highest incidence of AOM occurs between six and 24 months of age and declines until a small reversal is seen between five and six years of age, at the time of school entry.³ There tends to be a higher incidence of OME in younger than in older children, because the Eustachian tube in younger children is shorter, narrower, and more horizontal and the immune system is less developed. There is also increased incidence of OME associated with craniofacial anomalies, cleft palate, and Down syndrome. Middle ear effusion can result in temporary conductive hearing loss and negatively impact a child's cognitive, language, and emotional development.

More than 750,000 tympanostomy tube procedures are performed in children younger than age 18 annually in the US to address recurrent AOM or OME, making it one of the most common surgical procedures performed in children.⁴ By age 3, almost 7% of all children will have tympanostomy tubes.¹ Over 75% of tympanostomy tube procedures in the US are performed for children 12 years or younger, with 58% of tube procedures for children less than 5 years of age.⁴ Over 95% of tympanostomy tube insertion procedures in children are performed in the operating room (OR) under general anesthesia.⁴

The typical Myringotomy with Tympanostomy Tube placement (MTT) procedure in a child involves the following sequence of events:

- The child fasts from the evening before the procedure and is brought to the hospital or ambulatory surgery center.ⁱⁱ
- Premedication with oral midazolam may be provided to calm the child prior to parental separation.⁵
- After general anesthesia is attained, prophylactic analgesia to address post-operative pain such as rectal acetaminophen or intranasal fentanyl is typically provided.⁶
- Cerumen clearance is performed.

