11.4. Evaluation Methods

11.4.1. Diagnosis

Eligible subjects will be indicated for tympanostomy tube placement in alignment with the Clinical Practice Guideline.¹ The Clinical Practice Guideline for tympanostomy tubes in children was developed by a multidisciplinary panel, to provide clinicians with evidence-based recommendations on patient selection and surgical indications for and management of tympanostomy tubes in children.

According to the Clinical Practice Guideline, the decision to perform unilateral or bilateral tympanostomy tube insertion when unilateral OME is present should be based on caregiver preference [to accept or decline the risk of a second surgical procedure] and the likelihood of persistent OME developing in the opposite ear. For AOM with presence of effusion, the Guideline recommends bilateral TT placement for unilateral or bilateral disease. With the current care paradigm, a physician may perform bilateral tube placement for a unilateral condition to avoid the risk of multiple OR procedures and general anesthesia exposures if the second ear becomes affected. Since this study procedure is conducted in-office, it is proposed that the decision to perform unilateral or bilateral TT placement for AOM with effusion be based on caregiver preference and physician clinical judgment regarding the likelihood of disease developing in the opposite ear, similar to the Guideline recommendation for chronic OME.

The indications for tube placement have been clarified (as noted in italics) in instances where unilateral placement may be deemed appropriate by the physician and acceptable by the parent/guardian. The clinical indications for tube placement for children include:

- Bilateral TT insertion for bilateral otitis media with effusion (OME) for 3 months or longer (chronic OME) and documented hearing difficulties;
- *Unilateral or bilateral* TT insertion for unilateral or bilateral OME, *respectively*, for 3 months or longer (chronic OME) and symptoms that are likely attributable to OME

that include, but are not limited to, vestibular problems, poor school performance, behavioral problems, ear discomfort, or reduced quality of life;

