11.4.6. Audiometry

Audiometry will be employed to evaluate hearing status in each ear at screening (within 28 days prior to procedure) and at the 3-week post-procedure follow-up visit for all subjects age 4 years or older. Threshold testing will be conducted using air conduction and bone conduction at a minimum of 500, 1000, 2000 and 4000 Hz, and air conduction only at 8000Hz. Study sites will make efforts to measure hearing thresholds at all 5 frequencies. For younger subjects (less than 4 years of age), clinical study sites will attempt to collect audiometry at screening at a minimum of two frequencies for both air conduction (AC) and bone conduction (BC). The clinical study site audiologist will determine the most appropriate test method for each subject (visual reinforcement audiometry (VRA), conditioned play audiometry (CPA) or conventional audiometry). The method used at screening will be used for all follow-up assessments.

Audiometry is considered standard of care for this patient population and may be obtained prior to study informed consent as a screening assessment within 28 days prior to procedure.

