Possible	A clinical event, including laboratory test abnormality, with a reasonable time sequence to procedure, device or drug administration/exposure, but which could also be explained by concurrent disease, other interventions or drugs.
Not Related	A clinical event, including laboratory test abnormality, with a temporal relationship to procedure, device or drug administration/exposure which makes a causal relationship improbable, and in which concurrent disease, other interventions, other drugs or chemicals provide plausible explanations. A Not Related event may also not have a reasonable temporal relationship to procedure, device or drug administration/exposure.

*Causality definitions derived from WHO-UMC Causality Assessment Scale⁶⁸

Adverse Event Criteria – Hearing Loss

Audiometry will be used to assess changes to hearing thresholds for all ears. Investigators will diagnose post-treatment hearing impairment/loss if audiometry indicates a greater than 15-decibel (dB) change (worsening) in air conduction pure tone average for either ear. Classification of the level of hearing loss/impairment will be according to the American Academy of Audiology Childhood Screening Guidelines, as outlined in **Table 8**.^{69,70}

Table 8. Table of Hearing Threshold Change (Worsening) Classification

Level	Threshold Change
Slight	16-25 dB
Mild	26-40 dB
Moderate	41-55 dB
Moderately Severe	56-70 dB
Severe	71-90 dB
Profound	91 dB or greater

[figure not shown]

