14.3 Audiometric Assessments

Change in audiometric measurements (shifts) from baseline to the 3-week follow-up visit for subjects in the Safety Analysis Set will be presented using descriptive statistics (mean, SD, median, minimum and maximum). Shifts in air conduction (AC) and bone conduction (BC) hearing thresholds will be reported for each frequency (500, 1000, 2000 and 4000 Hz, and air conduction only at 8000Hz) and for each Cohort on a by-ear basis (treatment ears only). Shifts from baseline to each follow-up visit in air-bone gap (air conduction minus bone conduction) will also be reported for each frequency (500, 1000, 2000 and 4000 Hz) for each Cohort on a by-ear basis. Shifts in air conduction pure tone average (AC PTA), bone conduction PTA (BCA) and air-bone gap averages will be presented for each follow-up time point for each Cohort. For all PTA measurements, the PTA will be calculated by adding the threshold levels in decibels (dB) obtained at each frequency tested divided by number of frequencies tested.

Shift tables for air conduction pure tone averages greater than 15 dB (>15dB) by ear will be calculated, and presented for each Cohort for each follow-up time point.

Degree of hearing loss severity will be defined according to the protocol (slight through profound) and presented by subject for each Cohort and by relationship to study device, procedure or study drug.

Due to the differences in audiometric requirements for children dependent on age, all audiometry results will be presented by subjects less than 4 years of age, greater than 4 years of age, and overall.

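### The only visible numeric hearing-loss criterion uses air conduction, so where the tube closes an air-bone gap, ears with bone-conduction worsening are under-counted; add a by-ear bone-conduction shift table

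*Protocol*

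**What the plan says.** Protocol 12.4 has the investigator diagnose hearing impairment or loss "if audiometry indicates a greater than 15-decibel (dB) change (worsening) in air conduction pure tone average for either ear". Table 8 then grades the change, starting at 16 dB, which agrees with the trigger. No BC or air-bone-gap criterion is visible there.

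SAP 14.3 follows the same line: "Shift tables for air conduction pure tone averages greater than 15 dB (>15dB) by ear will be calculated". It takes its hearing-loss severity levels from the protocol.

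BC is measured. Protocol 11.4.6 states: "Threshold testing will be conducted using air conduction and bone conduction at a minimum of 500, 1000, 2000 and 4000 Hz". AC alone is tested at 8000 Hz. Audiometry is required at screening and "at the 3-week post-procedure follow-up visit for all subjects age 4 years or older"; for younger children the section describes only an attempt at screening.

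BC is also summarised. SAP 14.3 says "Shifts in air conduction (AC) and bone conduction (BC) hearing thresholds will be reported for each frequency", by ear, and adds shifts in the BC pure tone average (PTA) and in the air-bone gap. The statistics are mean, SD, median, minimum and maximum.

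On the disease, Protocol 6.1 says "Middle ear effusion can result in temporary conductive hearing loss". All four indications in Protocol 11.4.1 involve effusion, and one of them also requires documented hearing difficulties.

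**The concern.** The tube is placed to relieve the condition that can depress AC thresholds before treatment. By 3 weeks a working tube may improve AC whether or not the inner ear has changed. A rule based on AC worsening therefore compares the child with a baseline that the treatment is expected to improve, and that gain can offset a BC loss.

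The safety endpoint is the occurrence of adverse events by subject (Protocol 10.6, SAP 3.2). The protocol treats effects on the inner ear and its nerve as a possibility: section 8.0 points to ototoxicity information on lidocaine and epinephrine, and in-office subjects have an examination of cranial nerve VIII. An ear whose BC worsens while its air-bone gap closes may meet no numeric criterion, receive no Table 8 level and not appear in the table above 15 dB. The count of hearing-loss events could then be low partly because the tubes worked.

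**Working it through.** The plan gives no figure to reproduce, so the check is of the mechanism.

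**Inputs from the documents:** trigger of more than 15 dB worsening in AC PTA (Protocol 12.4); lowest grade 16 to 25 dB (Table 8); AC and BC both measured at 500, 1000, 2000 and 4000 Hz (Protocol 11.4.6).

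**Assumptions, because the documents give no values:** gap closure g of 0 to 30 dB; SD of the PTA change in one ear, s, of 5 to 10 dB.

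**Step 1, identity.** On matched frequencies, AC threshold = BC threshold + air-bone gap. So AC shift = BC shift − g, and the rule is met only if BC shift > 15 + g.

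- g = 0: BC must worsen by more than 15 dB
- g = 10: more than 25 dB
- g = 20: more than 35 dB
- g = 30: more than 45 dB

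**Step 2, a hypothetical ear.** Baseline AC 30, BC 5 (gap 25). At 3 weeks AC 25, BC 22 (gap 3). BC worsened by 22 − 5 = 17 dB and the gap closed by 25 − 3 = 22 dB, so the AC shift is 17 − 22 = −5 dB, an improvement. The rule is not met.

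**Step 3, chance that the AC rule flags a true BC loss b.** P = 1 − Φ((15 − (b − g))/s). Ranges run from s = 5 to s = 10.

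| g (dB) | b = 20 dB | b = 30 dB |
|---|---|---|
| 0 | 84% to 69% | 99.9% to 93% |
| 10 | 16% to 31% | 84% to 69% |
| 20 | 0.1% to 7% | 16% to 31% |
| 30 | 0.0% to 0.6% | 0.1% to 7% |

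The g = 0 row is also what a 15 dB cut-off applied directly to BC would give at the same s, whatever the gap closure. If closure itself varies with SD 10 and test noise has SD 5, then s = √(10² + 5²) = 11.2, and a 20 dB loss is flagged in 33%, 9% and 4% of ears at g = 10, 20 and 25. A BC cut-off with noise SD 5 flags 84%.

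**Step 4, cost in false flags.** For an unharmed ear, a BC cut-off of 15 dB is crossed with probability 1 − Φ(15/s): 0.1% at s = 5 and 6.7% at s = 10.

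**Step 5, do the planned summaries show it?** One ear with a 30 dB BC loss among 100 to 300 ears moves the mean by 30/100 = 0.3 to 30/300 = 0.1 dB, so the mean would not reveal it. The planned maximum would. Neither gives the number of affected ears or subjects.

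**Step 6, frequencies.** SAP 14.3 averages every frequency tested, so AC PTA can include 8000 Hz and BC PTA cannot. The identity in Step 1 is then only approximate for the PTAs as defined, and the planned AC and BC averages are not strictly comparable.

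**The case against.** A reader might infer that a BC loss cannot become an adverse event, or that the plan does not assess BC. The documents do not support either reading.

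- Protocol 12.1 includes as adverse events any clinically significant change found in the protocol evaluations, and BC audiometry is one of those. The ear category for other events in Table 5 has a grade for diagnostic observations alone. This route stands, but it rests on judgement without a number, beside an explicit numeric rule that an ear with improved AC does not meet.
- SAP 14.3 already plans BC, BC PTA and air-bone-gap shifts with the maximum, and hearing-loss severity by relationship to device, procedure or drug. SAP 21.0 lists all data by subject. An affected ear is therefore in the output; it is just not counted or flagged.
- The cranial nerve examination (Protocol 11.4.3) is the assessment assigned to finding adverse effects of the iontophoresis. Protocol 5.0 says only that audiometry assesses hearing. It goes too far to say that audiometry exists to detect inner-ear harm, or that Table 8 is wrong by g dB because it does not grade BC.

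The size is also open. Only one indication requires documented hearing difficulties, and bilateral tubes may be placed for unilateral effusion, so some ears may have little gap to close. Parts of Protocol 12.4 and 12.5 and of the SAP before section 14 are blacked out, so a further audiometric criterion cannot be excluded.

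Finally, a reader might conclude that the protocol should adopt a BC event trigger of more than 15 dB graded by Table 8. Nothing in the documents supports that threshold or grading for BC, and Step 4 shows that its false-flag rate depends strongly on an SD they do not give.

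**Conclusion.** The concern holds as a gap in counting and flagging. In the visible text, the only numeric hearing-loss criterion and the only by-ear table above 15 dB use AC PTA, and both under-count BC worsening in ears where the tube closes an air-bone gap. The direction follows from the identity for any g above 0. The size does not: the BC worsening needed is more than 25 to more than 45 dB for an assumed g of 10 to 30 dB, and stays at 15 dB where g is near 0. The detection percentages also rest on assumed SDs and are illustrations only.

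The reach is mainly children aged 4 and over, for whom 3-week audiometry is required. That includes the whole planned group of 102 children aged 5 to 12. The conclusion is subject to what the redacted text contains.

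**What to change.** In SAP 14.3:

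- Add a by-ear shift table for worsening of BC PTA beside the AC table, by cohort. Use the same display cut-off of more than 15 dB, or another that the sponsor justifies.
- For that comparison, compute AC PTA, BC PTA and air-bone gap on the same frequencies, 500 to 4000 Hz.
- For each ear flagged by either table, show whether BC moved or only the air-bone gap moved.

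In Protocol 12.4, state that ears flagged on BC are reviewed for an adverse event under section 12.1. Leave any numeric BC event threshold and its grading for the sponsor to set and justify.

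The cost is one table and one sentence, using data already collected. The downside is that some ears will be flagged through BC test-retest noise, which is why the flag leads to review and is not itself an event.
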